The MyChildCMC app will be uploaded into the Apple and Google Play app store for participants to download. As part of the app store publishing process, a legal privacy policy is required and was uploaded. In the privacy policy, there is a link where a potential participant may access the approved consent document to review before downloading the app.

Participant Recruitment and Enrollment: Screening will occur using inclusion/exclusion criteria. Potential participants will be directly approached or invited to participate in the study by project coordinators. Enrollment will be conducted in a private location in the clinic (e.g., exam room). Patient/parent dyads meeting eligibility and agreeing to participate will complete an informed consent document (for parents) and parental permission (for their child). Because the children participants have cognitive impairment, no assent will be obtained. All participants will receive general training on self-management of crosscutting symptoms, how to take measurement and how to identify acute deteriorations. Those randomized to MyChild^{CMC} will receive additional training about MyChild^{CMC} use.

While use of the children participants' PHI is required to achieve the aims and objects of this research, the children will not be asked to complete or perform any study related interventions or interactions.

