Randomization Procedure: Randomization will be performed using a computer-generated randomized allocation sequence made available online for the clinic care coordinator, and will be stratified by WeeFIM score as mild (18-54), moderate (55-90) and severe (\geq 91) disability, and age group (1-11 and 12-18 years), and performed using random permuted blocks to ensure assignment of subjects to the intervention and usual care groups is balanced over time. Participants randomized to MyChild^{CMC} will receive support to install the app, a temporary password (modified upon login) and full MyChild^{CMC} access. At the first login (in the clinic), the care coordinator will guide participants through baseline surveys and first assessment of crosscutting symptoms/ caregiver burden, thereafter caregivers will use the MyChild^{CMC} app over 3 months. All alerts about changing patient health status/caregiver burden will be directed to the care coordinator, who will follow-up with families to determine if an action, or a visit with a HCP or social worker is needed. The care coordinator will also access the dashboard to see participants not adherent with MyChild^{CMC} use and follow-up with those in need of supports. Participants randomized to usual care will receive general self-management education, be encouraged to monitor their child's symptoms/caregiver burden and identify deteriorations but without MyChild^{CMC}, and will complete surveys and provided incentive on the same schedule as the intervention group.

Data Collection: Upon first login, caregivers will complete a demographic survey (only once), including caregiver education level, a series of baseline surveys assessing the child (QOL) and caregiver (satisfaction, self-management skills, QOL and burden). Also, we will collect caregiver health literacy (only once) to be used in analysis of spec aims 3, and severity of child disability using WeeFIM which will be used in analysis of aims 2 and 3. 2 Baseline and follow-up surveys will be collected online by RedCAP within 3 months.

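### No allocation concealment is described, the sequence is given to the clinic care coordinator, and baseline CPCHILD is placed after assignment

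*Combined protocol and SAP*

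**What the plan says.** All references are to the Combined protocol and SAP.

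- **Mechanism.** Section 4, item 6, Randomization Procedure: randomization uses a "computer-generated randomized allocation sequence made available online for the clinic care coordinator". Allocation is stratified by WeeFIM category (three levels) and age group (two levels), and is "performed using random permuted blocks to ensure assignment of subjects to the intervention and usual care groups is balanced over time". Block sizes, the allocation ratio and the holder of the list are not given.
- **Baseline.** The same paragraph then covers app installation, the temporary password and full app access. Only after that, at the first login in the clinic, does it say that "the care coordinator will guide participants through baseline surveys and first assessment of crosscutting symptoms/ caregiver burden". The Data Collection paragraph also places the baseline surveys at first login, and lists the WeeFIM with them.
- **Follow-up by the same role.** Alerts from the app "will be directed to the care coordinator, who will follow-up with families to determine if an action" or a visit is needed.
- **Recruitment.** Item 6, Participant Recruitment and Enrollment: "Potential participants will be directly approached or invited to participate in the study by project coordinators". Item 4 gives identification, approach and consent to the study coordinator.
- **Use of baseline.** Item 9, Aim 2: the primary mixed model includes baseline CPCHILD total score, and its interaction with visit, as fixed effects.

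**The concern.** Two separate protections are in question.

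The first is concealment. If anyone who approaches or screens families can see the next assignment, a family can be invited, deferred or scheduled with that knowledge. The groups may then differ in prognosis in ways that no covariate fully captures, and analysis cannot repair this.

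The second is the baseline. The primary outcome is reported by caregivers, who know whether they have been given an app. If they complete baseline CPCHILD after learning their arm, with help from someone who also knows it, the covariate meant to remove chance imbalance may carry an effect of the assignment itself. Adjusting for it would then introduce bias.

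**Working it through.** **1. The plan's own figure.** Inputs from item 9, Aim 2, Statistical Power: SD 15.4, 220 randomized, up to 10% loss, two-sided alpha 0.05, difference 6.59 points, power at least 85%. Allocation of 1:1 is assumed.

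- Per arm: 220 × 0.9 / 2 = 99.
- SE = 15.4 × √(2/99) = 2.19.
- Power = Φ(6.59/2.19 − 1.96) = Φ(1.05) = 85.3%, or 85.0% with the noncentral t.

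The stated power reproduces. It does not depend on concealment; it is used here only for the SE.

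**2. Who can see what.**

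| Question | What the document gives |
|---|---|
| What is made available? | The sequence, online |
| To whom? | The clinic care coordinator |
| Whole list or one assignment at a time? | Not stated |
| Who approaches and consents? | Project and study coordinators |
| Can they see the sequence, or act as care coordinator? | Not stated |
| Block sizes, fixed or varied? | Not stated |

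**3. Order of steps.** Item 6 asks for procedures in chronological order. The text gives screening, consent, randomization, app installation and access, then baseline surveys at first login. Stratified allocation needs the WeeFIM category and age before an assignment can be drawn, so the stratum must in practice be known by then, although no lock is described. Nothing similar forces baseline CPCHILD to come first. The usual-care arm completes surveys on the same schedule, so the order is open there too.

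**4. What a shifted baseline does.** With equal SDs at baseline and follow-up (an assumption), the slope on baseline equals the correlation. The power paragraph uses 0.5 as its example. If knowing the arm shifts mean baseline by d points in one arm only, the adjusted difference moves by 0.5 × d in the opposite direction. A shift of 1 point gives 0.5 × 1 = 0.5 point, or 0.5/6.59 = 8% of the planned difference. The document gives no value for d.

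**5. Purely hypothetical figures for lost concealment.**

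- *Predictability.* Suppose assignments are released singly, but blocks have a fixed, known size 2m and someone tracks past assignments within each of the 3 × 2 = 6 strata. The share of assignments that is certain is 1/(m+1): 33% for blocks of 4 and 25% for blocks of 6. Best-guess success is 71% and 68%, against 50% by chance. With the whole list visible, every assignment is known.
- *Bias.* Suppose a share f of dyads is steered, with a 0.5 SD difference in prognosis that baseline does not capture. Bias = f × 0.5 × 15.4, and type I error = P(|Z + bias/2.19| > 1.96).

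| f | Bias (points) | Share of 6.59 | Type I error |
|---|---|---|---|
| 10% | 0.77 | 12% | 6.4% |
| 20% | 1.54 | 23% | 10.8% |

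Block size, f and the 0.5 SD shift are all assumed.

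**The case against.** The strongest reply is that making a sequence available online is also how one might loosely describe a web service that releases one assignment for each registered participant. The text does not choose between that and a readable list. A reader might infer that upcoming assignments are open to view; the document does not establish this. This part of the reply stands.

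Second, steering needs foreknowledge in whoever recruits, and recruitment is assigned to differently named roles. This stands in part. The document does not say that the roles are held by different people, or that recruiters are barred from the list. Section 8, item 1 has the clinical research coordinator both consenting participants and collecting data, while item 6 has the care coordinator guiding baseline surveys, so the division of tasks is unclear.

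Third, the care coordinator's handling of alerts and the adherence dashboard may look like a breach of concealment or biased outcome assessment. It is neither: it is delivery of the app, and the surveys are collected online through REDCap. That role is no part of the case here.

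Fourth, the bias figures assume that baseline captures none of the shift, although the primary model adjusts for baseline CPCHILD, WeeFIM and age strata. This stands, and the figures cannot be read as a forecast.

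None of these replies answers the order of steps. Even with perfect single release, baseline CPCHILD is described after assignment.

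**Conclusion.** The point holds in two parts.

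1. The protocol describes no allocation concealment and, read literally, gives the sequence to a member of the clinic staff. Whether anyone could actually foresee assignments is unknown. The tempting conclusion that allocation is unconcealed and recruitment open to selection bias goes further than the text.
2. As written, baseline CPCHILD can be collected with the arm known, in a trial where caregivers know their arm and report the primary outcome. This follows from the described sequence of steps and does not depend on how the list is released.

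No bias can be sized from the document. The 0.5 point per point of baseline shift rests on the plan's example correlation and on equal SDs. The 33% and 25% predictability and the 6.4% and 10.8% type I error rest entirely on assumptions. They show why the safeguard is worth having, not what will happen. The change is worth making because it is specific, reduces the risk of bias and costs little.

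**What to change.** Replace the allocation sentence in Section 4, item 6 with text along these lines:

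> A central web system holds the allocation sequence. It releases one assignment at a time, only after consent, eligibility, WeeFIM and age stratum, and baseline CPCHILD have been entered and locked. No one who recruits, assesses or supports participants can see the sequence. Block sizes vary at random and are not disclosed to the clinic.

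Name the role that generates and holds the list. Amend the first-login sentence and the Data Collection paragraph so that, in both arms, baseline CPCHILD and the WeeFIM come before assignment.

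**Cost.** A short protocol change and configuration of the online randomization already planned. Baseline surveys must be finished before assignment, which lengthens the enrolment visit or delays assignment. If enrolment has begun, which the Consent Process section's provision for re-consenting patients over 18 suggests is possible, the change can apply only to later participants. If single release is already intended, the concealment part costs only the wording.

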Validated surveys will be used to collect data, including a 37-item Caregiver Priorities and Child Health Index of Life with Disabilities (CPCHILD) Questionnaire (child QOL), 12-item Parent satisfaction questionnaire, which includes one open-ended question assessing participant's perception of burden related to MyChild^{CMC} use, 13-item Patient Activation Measure (caregiver self-management skills), 12-item Short Form health survey (caregiver QOL), and a 6-item Newest Vital Sign (NVS) for caregiver health literacy. At each QOL, we will also collect caregiving burden summary over the past month for both the intervention and control groups. All HCP caring for CMC during the study period will be surveyed at the end of the study to assess their satisfaction with care using the 6-item HCP Satisfaction Questionnaire. ED and hospital admissions will be collected using the Intermountain enterprise data warehouse (EDW),152 an integrated database linking data of 22 hospitals in Utah and Idaho. Intermountain Healthcare provides services for > 95 % of children in Utah.

7. Are all procedures for research purposes only (non-standard or non-standard of care procedures)? Yes O No

If no, list the procedures that are performed for research purposes only (non-standard or non-standard of care procedures):

8. Is there a safety monitoring plan for this study?

🔿 Yes 🌑 No

9. Provide a summary of the statistical methods, data analysis, or data interpretation planned for this study. Factors for determining the proposed sample size (e.g., power) should be stated.

Data Analysis. We will assess Feasibility, using family's participation, retention, adherence, and dropout rates. We will also assess parent responses to interactive activities such as response to reminders and alerts, to inform the future enhancement, and the appropriateness of the alerts triggered by the MyChild^{CMC} app. Preliminary Impact: The primary outcome is QOL score, obtained at baseline, 1 and 3 months. Secondary outcomes are QOL sub-domains (comfort, emotions, communication and social interaction, health, and overall QOL), ED/hospital admissions and caregiver satisfaction. Further detail will be provided during phase 2.

AIM 2

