The primary analysis of the CPCHILD total score will be performed by applying a linear mixed effects model to compare the mean QOL score over the 3, 6, 9 and 12-month assessments between the intervention and control groups. The mixed effects model will incorporate an unstructured covariance matrix to account for serial correlation within the same patients, and will include fixed effect terms for the randomized treatment assignment, the baseline CPCHILD total score, Clinic, and the WeeFIM and age group randomization strata as well as interaction terms between each of these factors and follow-up visit. Adjustment for the baseline CPCHILD total score will account for any baseline imbalances in the outcome variable and regression to the mean, thereby increasing statistical power. In addition to the primary comparison of the mean CPCHILD total score over all 4 follow-up assessments between the randomized groups, secondary contrasts will be constructed to estimate treatment effect on the mean total score at each individual follow-up visits and to compare the size of the treatment effects between different follow-up visits to determine if the treatment effect attenuates or increases over time. Secondary outcomes will be compared between the randomized groups using similar linear mixed models for numeric outcomes (e.g., other CPCHILD subscales, caregiver/HCP satisfaction, PAM score, and burden score) or generalized linear models with use of robust empirical standard errors for categorical outcomes. Similar analysis will be used to compare caregiver burden subscales (stress and coping). The rate of ED visits and hospital admissions will be compared between randomized groups using negative binomial regression, possibly augmented to account for 0-inflation if the proportion of subjects with 0 ED events or hospitalizations exceeds that accounted for by the negative binomial model

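### Baseline CPCHILD, a covariate in the primary model, is written as completed after randomisation in the app arm and is not placed before allocation in either arm

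*Combined protocol and SAP*

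**What the plan says.** Section 4 (Study Information), item 6, asks for the procedures in chronological order. The Randomization Procedure paragraph describes a computer-generated sequence "made available online for the clinic care coordinator", stratified by WeeFIM score and age group. Families randomised to the app "will receive support to install the app, a temporary password (modified upon login" and then have full access. The paragraph continues: "At the first login (in the clinic), the care coordinator will guide participants through baseline surveys".

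The Data Collection paragraph repeats the timing. Upon first login, caregivers complete a demographic survey and "a series of baseline surveys assessing the child (QOL) and caregiver". The child instrument, named just below, is the "37-item Caregiver Priorities and Child Health Index of Life with Disabilities (CPCHILD) Questionnaire (child QOL".

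On mode, "Baseline and follow-up surveys will be collected online by RedCAP within 3 months", with no restriction to one arm. Usual-care families "will complete surveys and provided incentive on the same schedule as the intervention group".

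The AIM 2 Data Analysis text enters the baseline CPCHILD total score as a fixed effect, with a visit interaction, in the primary mixed model. The stated reason is that "Adjustment for the baseline CPCHILD total score will account for any baseline imbalances in the outcome variable and regression to the mean".

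**The concern.** A baseline covariate can be adjusted for safely when treatment assignment cannot have affected it. CPCHILD is reported by the caregiver. In the written order, an app-arm caregiver answers it after learning the arm, while logging in to the app, guided by a coordinator who also knows the arm. If that knowledge raises or lowers the answers, the app-arm baseline carries an effect of allocation. The model would treat the resulting difference between arms as chance imbalance and adjust for it, which biases the primary treatment effect.

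Usual-care families have no app login, so an instruction to follow the same schedule does not say when their baseline falls relative to allocation, or whether anyone guides it. The arms could therefore differ in both timing and help.

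**Working it through.** **Order of events.** Four other places could date the baseline:

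| Place | What it adds | Does it put CPCHILD before allocation? |
|---|---|---|
| Section 4, item 4, and Consent Process (training and log-in after enrolment) | Mentions neither baseline surveys nor randomisation | No |
| Section 4, item 6 (stratification by WeeFIM) | WeeFIM must be known before allocation; no collection time is given, and it is listed apart from the QOL surveys | No |
| Section 6, item 4 (payment) | Ties baseline surveys to enrolment | No; allocation is not mentioned |
| Section 6, item 4 (stethoscope) | Handed over at the end of enrolment and baseline; elsewhere in the item it is for the app arm only | Fits one visit, in either order |

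The only explicit timing is first login, stated twice.

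**The plan's own figures.** Inputs from AIM 2 Statistical Power: 220 randomised, 10% loss, SD 15.4, two-sided alpha 0.05, power 85%, example correlation 0.5. Equal allocation is assumed, since no ratio is stated.

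- Per arm: 220 × 0.9 / 2 = 99.
- Unadjusted SE: 15.4 × √(2/99) = 2.189.
- Adjusted SE: 2.189 × √(1 − 0.5²) = 1.896.
- Detectable difference, normal approximation: (1.960 + 1.036) × SE = 6.56 unadjusted and 5.68 adjusted. The plan gives 6.59 and 5.73, so its figures reproduce closely.

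**Effect of a shifted baseline (illustration).** Let b be the shift in the app-arm mean baseline caused by knowing the arm. The adjusted effect is (difference in follow-up means) − slope × (difference in baseline means). With equal SDs at the two times, the slope equals the correlation, 0.5.

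- Shift gone by follow-up: bias = 0 − 0.5b = −0.5b.
- Same shift persists at follow-up, written order: bias = b − 0.5b = +0.5b.
- Same shift at follow-up only, baseline taken before allocation: bias = b.
- No baseline term in the model: bias = 0 if the shift has gone, b if it persists.

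Type I error = Φ(−1.96 + |bias|/SE) + Φ(−1.96 − |bias|/SE):

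| Assumed size of b (points; SD) | Written order: size of bias | Written order: type I error | Clean baseline, shift at follow-up: type I error | No baseline term, persistent shift: type I error |
|---|---|---|---|---|
| 0 | 0 | 5.0% | 5.0% | 5.0% |
| 1.54 (0.1) | 0.77 | 6.9% | 12.8% | 10.8% |
| 3.08 (0.2) | 1.54 | 12.8% | 36.9% | 29.1% |
| 4.62 (0.3) | 2.31 | 23.0% | 68.3% | 56.0% |

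The written-order columns apply to both the transient and the persistent shift; only the sign of the bias differs. With no baseline term and a transient shift, type I error is 5.0%. Simulation at b = 3.08 (20,000 trials per scenario) agrees to within about one percentage point.

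**Power for a true 5.73-point difference.** With b = 0: Φ(5.73/1.896 − 1.96) = 85.6% adjusted, and Φ(5.73/2.189 − 1.96) = 74.5% unadjusted. With a bias of 1.54 points against the true effect: Φ((5.73 − 1.54)/1.896 − 1.96) = 59.9%.

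**Sensitivity to the correlation.** At b = 2, written-order type I error is 6.0%, 8.2% and 14.6% for correlations of 0.3, 0.5 and 0.7.

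All of this uses a single follow-up, so it does not depend on which follow-up schedule applies.

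**The case against.** **Position in the text is weak evidence of order.** Item 6 mentions app-specific training before it describes randomisation, and mentions WeeFIM collection after it, although WeeFIM must come first. The first-login sentence in Data Collection is not limited to one arm, and RedCAP collection does not need the app. The payment text fits a baseline-first visit equally well. This stands as a caution about what was actually done: the wording may be loose drafting. It does not supply a statement that CPCHILD precedes allocation, and the in-clinic login sentence directly follows the grant of access to randomised families.

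**The link to the primary model crosses a schedule conflict.** Item 6 describes three months of app use, and the first analysis paragraph of item 9 uses baseline, 1 and 3 months with no baseline adjustment stated. The adjusted model is for 3, 6, 9 and 12 months. The conflict is real, but the two share the WeeFIM and age-group strata and the same instrument, and the document describes no other baseline procedure.

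**The size is wholly assumed.** This is correct. The baseline comes before any app use, so only expectation could act, and zero is plausible. The slope is also approximate, because the model adjusts for clinic and strata, and the error rates are for one follow-up rather than the mean of four.

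**The fix may not reduce total bias.** This also stands. If arm-aware reporting persists at follow-up, a clean baseline leaves the full b instead of half of it. That bias belongs to outcome reporting. Having a contaminated covariate partly cancel it would be accidental, and the same covariate creates bias when the shift is transient.

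**Conclusion.** The concern holds. As written, the app arm completes the primary-model covariate after randomisation with an allocation-aware coordinator, and nothing in the available text places it before allocation in either arm. This should be fixed, with medium confidence: the wording is clear, but actual conduct is unknown.

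No bias size can be derived from the documents. At the assumed shifts of 0.1 to 0.3 SD, the written order gives a bias of 0.77 to 2.31 points. Its direction depends on the sign of the shift and on whether the shift lasts to follow-up. These figures rest on equal allocation, equal SDs, a correlation of 0.5 and a single follow-up; with no shift there is no bias. They show why the order matters and do not predict this trial's error rate.

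**What to change.** State in Section 4, item 6 that, after consent:

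1. WeeFIM and all baseline surveys, including CPCHILD, are completed in both arms by the same RedCAP route and with the same coordinator help.
2. The online system releases the allocation only once these are recorded as complete.
3. App installation, password, app training and the first symptom and burden assessment then follow for the app arm.

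This costs one completeness check and a reordering within the same enrolment visit. The sample size does not change, and no extra data are needed for families not yet enrolled.

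If families were already enrolled in the written order, record for each whether baseline preceded allocation, and add a sensitivity analysis without the baseline CPCHILD term. This does need family-level records. State the analysis's limits: in the single-follow-up calculation its SE is about 2.19 against 1.90, and its power at 5.73 points is about 74% against 86%. It does not address arm-aware reporting at follow-up.

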Focus Groups and Usability testing session will generate valuable input/feedback about the how the MyChild^{CMC} tool will be develop and used. We will add IRB amendments for the parent permission consent when we are ready to add participants. Because we cannot anticipate all the changes we have just added the first consent (attached) for the Focus Group.

Focus Groups: three focus groups (6-8 parent participants per session) with 24 parent participants in Year 1 and two usability testing cycles, each assessing 6 parent participants (for a total of 12 parent participants) in Year 2. Participants will receive participant remuneration equivalent to a \$50 gift card after participating in each focus group and usability testing. The PI and all members of the Research Team will adhere to all University of Utah Payments to Human Research Participants rules and regulations.

A written flyer describing the study will be displayed in Comprehensive Care Clinic at Primary Children's Hospital ([name] (Co-I) is the medical director in this clinic) to recruit potential participants. If a parent is interested in participating, a research staff will approach them to consent and enroll in the study.

Patients/Parents will be identified by the CMC study coordinator ([name], [name]) in CMC clinics or the inpatient at PCH, or those who express interest in participating in the study after seeing the written flyer posted in the clinic. The family will then be approached by the study coordinator to participate in the study if they meet criteria. The study coordinator will obtain a signed consent form from the patient/parent to participate in the study. After enrollment, patients/parents will be trained during the formal education about the MyChild^{CMC} app, the dynamic run chart report (including definitions of the scale and colors) as well as the Patient Portal. Participants will download the MyChild^{CMC} app onto their smartphones and create a log-in account. Patients will be trained in how to use the system. Patients also will be encouraged to bring the form to their primary care provider at the time of follow-up visit. A contact number will available for questions and support regarding any technical aspects of the MyChild^{CMC}.

5. How will consent be obtained?

Informed Consent Process (with or without a document)

6. Describe all the procedures chronologically, from screening/enrollment through study closeout, which will be completed in the research project.

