Data Analysis: The primary outcome is the CPCHILD total score, which will summarize the child's QOL at baseline, and at 3, 6, 9 and 12 months of follow-up. Secondary outcomes include additional CPCHILD sub-domains beyond the total CPCHILD (comfort and emotions; communication and social interaction; health; and overall QOL), child ED/hospital admission, and caregiver satisfaction, self-management skills, caregiver burden, and HCP satisfaction. The primary and secondary analyses will be performed in accordance with intention-to-treat, with patients analyzed in accordance with the randomized treatment assignment irrespective of compliance. Numeric outcome variables exhibiting positive skewness may be transformed to better approximate normality. Analyses will be performed with SAS version 9.4 or higher. Standard statistics including means, standard deviations, medians, and interquartile ranges for continuous variables and frequencies and percent for categorical variables will be used to compare characteristics of randomized vs. non-randomized patients and to compare baseline characteristics between randomized groups. Open-ended questions of caregiver and HCP satisfaction will be analyzed using standard qualitative analysis as described in Aim 1.

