IRB_00088596 Title: SELF-MANAGEMENT INTERVENTION FOR CHILDREN WITH CHRONIC MEDICAL COMPLEXITY Description of Study:					

Our Specific Aims are: Aim 1. Partner with caregivers to develop the MyChild^{CMC} application: 1.a. Assess caregiver needs, preferences and capability for CMC self-management through focus groups; 1.b. Develop the MyChild^{CMC} application to engage caregivers in ongoing monitoring of crosscutting symptoms, alerting the clinic care coordinator if a child's symptoms worsen to prompt timely interventions, and monitoring caregiver

burden to prevent burnout; and 1.c. Explore the MyChild^{CMC} usability to incorporate user suggestions and enhance user acceptance and performance of the application. Aim 2. Assess the impact of the MyChild^{CMC} app by comparing outcomes for the: 2.a. child (QOL and ED/hospital admissions); 2.b. caregiver (satisfaction, self-management skills, QOL and burden); and 2.c. health care provider (satisfaction), between child/caregiver dyads randomized to either MyChild^{CMC} or usual care. Aim 3. Assess whether the effect of the MyChild^{CMC} intervention on child outcomes varies across caregiver characteristics (ethnicity, education, health literacy, and insurance).

Assigned IRB Coordinator: [name] Anticipated Length of Study: 5 years

1. Describe how this study furthers excellence in the provision of health care for children.

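### HCP satisfaction is to be compared between randomised arms, but the one end-of-study HCP survey has no stated link to an arm and cannot supply the baseline or visit terms of the model

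*Combined protocol and SAP*

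**What the plan says.** **Aim.** The Specific Aims under Description of Study set Aim 2.c as a comparison of "health care provider (satisfaction), between child/caregiver dyads randomized to either" the app or usual care. The same aim under 1. Study Introduction, item 6, is broken in the text available, so only the former place is legible.

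**Outcome and analysis set.** Section 4, item 9, AIM 2 Data Analysis ends its list of secondary outcomes and goes straight on to the analysis rule: "caregiver burden, and HCP satisfaction. The primary and secondary analyses will be performed in accordance with intention-to-treat". The rule is worded for patients; nothing is said about how it applies to a provider.

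**Model.** The same section compares secondary outcomes between the randomised groups by "similar linear mixed models for numeric outcomes (e.g., other CPCHILD subscales, caregiver/HCP satisfaction, PAM score, and burden score". The primary model has terms for treatment, baseline CPCHILD score, clinic and the WeeFIM and age strata, the interaction of each with visit, and an unstructured covariance over the 3, 6, 9 and 12-month assessments.

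**Data.** Section 4, item 6, Data Collection gives the only HCP measurement: "All HCP caring for CMC during the study period will be surveyed at the end of the study to assess their satisfaction with care", by a 6-item questionnaire.

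**Randomisation.** Section 4, item 6, Randomization Procedure uses "random permuted blocks to ensure assignment of subjects to the intervention and usual care groups is balanced over time", and allocation "will be stratified by WeeFIM score as mild (18-54), moderate (55-90) and severe" disability and by age group. Provider is not a stratum.

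**The concern.** A comparison between arms needs each response to carry an arm. Children have one by randomisation, and caregivers take their child's. A provider has one only if every enrolled child in that provider's care was allocated the same way. The plan describes one survey per provider and gives no rule for linking the score to an arm.

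At stake is one of the three named parts of Aim 2. Without a rule, the analyst must decide after the data are in which providers to keep and how to label them, and the result could then be reported as a randomised intention-to-treat comparison.

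There is a second, separate mismatch. The primary model relies on a baseline value and repeated follow-up visits. A survey given once, at the end, has neither.

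**Working it through.** **1. Figures in the plan.** AIM 2 gives a sample size for the CPCHILD total score only. It reproduces: 2 × (1.960 + 1.036)² × (15.4 / 6.59)² = 98.1, so 99 per arm; 198 / 0.90 = 220. For HCP satisfaction the documents give no sample size, no number of HCPs, no number of HCPs per child and no number of enrolled patients per HCP.

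**2. Which model terms the HCP survey can supply.**

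| Term | One form per HCP | One form per enrolled patient |
|---|---|---|
| Randomised arm | only if all of the HCP's enrolled patients share an arm | yes |
| WeeFIM and age strata | attributes of the child, so only if the patients agree | yes |
| Baseline score | no | no |
| Visit terms and unstructured covariance | no | no |
| Term for patients sharing a provider | not applicable | needed, not in the model |

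The arm label therefore depends on how the form is completed. The absence of a baseline and of visits does not.

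**3. How often an HCP has patients in both arms.** Let m be the HCP's number of enrolled patients. Assume 1:1 allocation, independent of provider (the ratio is not stated). The chance that not all m fall in one arm is 1 − 2 × 0.5^m. For 2:1 allocation it is 1 − (2/3)^m − (1/3)^m.

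| m | 1:1 | 2:1 |
|---|---|---|
| 2 | 1 − 0.500 = 50% | 44% |
| 3 | 1 − 0.250 = 75% | 67% |
| 5 | 1 − 0.0625 = 94% | 86% |

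Blocking changes little unless patients share a block. With exactly 110 of 220 in each arm and m = 2, the chance is 1 − 109/219 = 50.2%. For two patients from the same block of four it is 4/6 = 67% (block size is not stated, so four is an assumption).

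These are chances for a given m. The documents do not give m, so no overall share of HCPs can be worked out.

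**4. Size needed for a within-provider comparison.** Suppose each HCP with patients in both arms rated the arms separately. For a paired difference of 0.5 SD, two-sided 0.05 and 80% power, n ≈ (1.960 + 0.842)² × 2(1 − ρ) / 0.5², where ρ is the assumed within-provider correlation. At ρ = 0.5 this is 7.85 × 1 / 0.25 = 31.4, and the paired t test raises it to 34. At ρ = 0.3 it is 7.85 × 1.4 / 0.25 = 44.0, giving 46. At ρ = 0.7 it is 7.85 × 0.6 / 0.25 = 18.8, giving 21.

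**The case against.** The strongest reply is that the questionnaire is not shown. Aim 2.c speaks of a comparison between dyads, and the intention-to-treat rule speaks of patients; both would fit a form completed once per enrolled child. Under that reading every score has an arm. This stands as a possibility, and the point is conditional on it. But no per-patient form is described, and even with one the baseline and visit terms have no data and ratings by the same HCP are treated as unrelated.

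A second reply is that a similar model need not be identical, so an analyst would simply leave out the terms that do not apply. That is reasonable for the baseline and visits, though it should be written down. It does not create an arm label.

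A third is that this is a summary on an ethics form which promises more detail in phase 2. That promise closes the pilot paragraph, whose outcome list omits HCP satisfaction. The AIM 2 text already names the outcome and its model.

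Four stronger inferences are tempting, and the documents do not support them:

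- That HCPs do treat children in both arms. This is likely when patients are randomised at one hospital without regard to provider, but it is not stated. Providers with patients in only one arm may exist: "Patients also will be encouraged to bring the form to their primary care provider at the time of follow-up visit" shows that children also have providers of their own.
- That Aim 2.c cannot be answered at all from HCPs with patients in both arms. Their scores could be related to the share of their patients using the app. The plan does not specify that analysis, but the data would not be useless.
- That HCPs with patients in one arm would mainly be those with one or two enrolled patients. That depends on HCP numbers and caseloads, which are not given.
- That analysts would copy each HCP's score to that HCP's patients and so dilute an effect. Nothing in the documents proposes this.

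**Conclusion.** The point holds in conditional form. If each HCP completes one form, as the text reads, an HCP with patients in both arms has no arm label and the stated between-arm comparison cannot be fitted to that HCP. This affects 50%, 75% or 94% of HCPs with 2, 3 or 5 enrolled patients, assuming independent 1:1 allocation. If the form is completed per patient, which is neither stated nor excluded, the label exists and the gap is one of wording and clustering.

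Under either reading, a single end-of-study survey cannot support the baseline, visit and unstructured-covariance terms of the primary model.

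The primary outcome and its sample size of 220 are unaffected. This is a minor correction to a secondary outcome, but one to the plan as written, because the specified analysis does not match the data described.

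**What to change.** Choose one of three and state it.

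1. **Describe only.** Report the HCP survey as a summary of one group. This sits naturally beside the plan's existing provision, "Open-ended questions of caregiver and HCP satisfaction will be analyzed using standard qualitative analysis as described in Aim 1". Remove HCP satisfaction from the randomised secondary outcomes and from the mixed-model list in AIM 2 Data Analysis, and restate Aim 2.c wherever it appears. Cost: wording only, but the between-arm HCP comparison is given up.

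2. **Rate each arm separately.** Ask every HCP with patients in both arms to answer the six items once for MyChildCMC patients and once for usual-care patients. Analyse the paired within-provider difference, or both ratings with an arm term and a provider random intercept, without baseline or visit terms. Cost: six more items per HCP and ratings made knowing the arm. HCPs with patients in one arm only give no within-provider difference. About 34 HCPs with patients in both arms are needed for 80% power at 0.5 SD if the within-provider correlation is 0.5 (46 to 21 for correlations of 0.3 to 0.7). With fewer, the first choice is more realistic.

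3. **Confirm a per-patient form.** If that is what is meant, say so under Data Collection. For this outcome specify a single-time-point model with arm, the randomisation strata and a provider random effect, and no baseline or visit terms. Cost: wording in Data Collection and AIM 2 Data Analysis.
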